- 13 Iron-related parameters/markers of erythropoiesis sampled at pre-dose and 2 hours post-morning dose include total serum iron, serum ferritin, transferrin, TSAT, hepcidin, and erythropoietin. At Visit V1, serum ferritin, and TSAT will be sampled for exclusion criteria only.
- 14 PK samples are collected on Visit V4 at pre-dose, and 2 hours (±15 minutes), 4 hours (±30 minutes), and 6 hours (±30 minutes) post-dose.
- 15 At Visit V2, the subject will be asked for VOC episodes within the last 8 weeks. At Visits V3, V4, V5, and V6, the subject will be asked for VOC episodes (number of events and pain intensity (NRS: 0-10) compared to historical VOC episodes) since previous visits. Visceral infarctions will be assessed as per standard of care.
- 16 For more details see the respective visit in Section 8.

Notes: abs=Absolute; ASCQ-Me=Adult Sickle Cell Quality of Life Measurement System; C=Central laboratory assessment; CHCM=Corpuscular Hb concentration mean; ECG=Electrocardiogram; EoS=End of study; EoT=End of treatment; ET=Early termination; Hb=Haemoglobin; HbsAg=Hepatitis B surface antigen; HBV=Hepatitis B virus; hCG=Human chorionic gonadotropin; Hct=Haematocrit; HCV=Hepatitis C virus; hsCRP=High sensitivity C-reactive protein; IL=Interleukin; IMP=Investigational medicinal product; IWRS=Interactive web response system; L=Local laboratory assessment; LDH=Lactate dehydrogenase; MCH=Mean corpuscular Hb; MCHC=Mean corpuscular Hb concentration; MCV=Mean corpuscular volume; NRS=Numerical rating scale; PK=Pharmacokinetic; RBC=Red blood cell; RDW=Red blood cell distribution width; SCD=Sickle cell disease; sP=Soluble platelet; sVCAM=Soluble vascular cell adhesion molecule; TNF=tumour necrosis factor; TSAT=Transferrin saturation; V=Visit; VOC=Vaso-occlusive crises; WBC=White blood cell.

VIT-2763-SCD-202, Version 4.0
16 March 2023
Page 22 of 108

TABLE OF CONTENTS

	Page
SIGNATURE PAGE	2
INVESTIGATOR AGREEMENT AND SIGNATURE PAGE	6
SYNOPSIS	7
TABLE OF CONTENTS	23
LIST OF TABLES	27
LIST OF FIGURES	28
LIST OF ABBREVIATIONS	

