Following multiple oral dose for 7 days up to 120 mg every 12 hours there was no apparent change in absorption and accumulation was minimal. The apparent volume of distribution following single oral administration was moderate ranging from 64.3 to 145 l indicating moderate distribution to tissues. The geometric mean $t_{1/2}$ ranged from 1.9 to 5.3 hours following single oral dosing and from 2.07 to 3.80 hours on Day 1 and from 2.61 to 5.26 hours on Day 7 following repeated dosing.

Following both single and multiple dosing, a temporary decrease in mean serum iron levels and a temporary decrease in mean calculated % TSAT was seen at all VIT-2763 dose levels

between 4-hours and 12-hours post-dose. Following both single and multiple dosing, a temporary increase in mean serum hepcidin levels was seen at doses of 60/120/240 mg for single dosing and at all VIT-2763 multiple dose levels. Maximum mean serum hepcidin levels were observed between 1-hour and 4-hours post-dose for the highest single dose levels of 60 mg, 120 mg, and 240 mg, and for all 4 multiple dose levels. No dose related effects were observed with respect to serum ferritin, serum transferrin, serum erythropoietin and serum soluble transferrin receptor levels on both Day 1 and Day 7.

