1.4.2 Study VIT-2763-THAL-201

A Phase 2a trial has recently been completed (Q4, 2021), with study sites in the EU, Thailand, Israel, and Lebanon. Study VIT-2763-THAL-201 was a double-blind, randomised, placebo-controlled, parallel group trial evaluating the safety, tolerability, PK, PD, and preliminary efficacy of multiple doses of VIT-2763 in 25 adult subjects with non-transfusion dependent (NTD) thalassaemia. After database lock, topline results were generated January 2022.

The primary safety endpoints were reported or observed AEs and SAEs, changes in vital signs (blood pressure and pulse rate and respiratory rate), clinical laboratory safety tests (haematology, serum biochemistry, coagulation, and urinalysis), 12-lead ECG, and physical examination findings.

The first subject in Study VIT-2763-THAL-201 was enrolled in June 2020 (in Lebanon). Blinded interim results in 10 adult subjects were obtained in Q1/2021 and revealed no safety concerns as judged by the Safety Review Committee; topline results of all subjects have been analysed (Q1/2022) (Investigational New Drug (IND), Section 1.11.4), demonstrating that VIT-2763 was safe and well tolerated. The interim analysis also showed that VIT-2763 had significant target engagement with FPN, lowering consistently and throughout the treatment period serum iron and TSAT. The study could not show significant changes from baseline in clinically relevant blood biomarkers such as Hb, RBC count, MCHC, MCV, reticulocyte counts and reticulocyte Hb content. Learnings from Study VIT-2763-THAL-201 suggest that TID dosing may be required to achieve the full efficacy of vamifeport, and PK and PD samples will needed to be collected at additional time points to fully understand the effects of vamifeport. These results led to the amendment of this study protocol (see Section 2.3).

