Animal models of SCD with 2 administrations of VIT-2763 during the day, showed significant clinical benefit. However, data obtained from the VIT-2763-THAL-201 study indicate that higher doses or more frequent dosing is required to sustain iron restriction throughout the whole dosing period. Signs of chronic excessive PD effects (i.e., anaemia) can be detected early on; haematological safety parameters will be monitored throughout the study (every 2 weeks). The selected VIT-2763 dose levels and dosing frequencies in this Phase 2a exploratory study are considered to be safe and are intended to explore at its best the potential therapeutic PD range of VIT-2763 in this patient population. Different levels of serum iron restriction (doses of 120 mg, 240 mg and 360 mg) and different fluctuations of induced peak and trough serum iron throughout a 24-hour period (BID and TID) are explored. It is still unknown if a more sustained serum iron restriction (TID) or more fluctuating (BID) serum iron levels translate into better clinical outcomes in SCD. That is the reason why in the current protocol a broad range of doses and dosing regimens is explored.

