8.4 Visit 4 (Day 28±4 Days)

The subject may attend the V4 visit in the afternoon/evening before to facilitate compliance and V4 visit procedures. Note: A planned overnight stay the day before Visit V4 does not fulfil the seriousness criteria of an SAE unless there is a medical requirement. The following activities will be performed at Visit V4:

- Perform physical examination. Body systems to be assessed include general appearance, head (eyes, ears, nose, and throat), cardiovascular, respiratory, abdominal, musculoskeletal, neurological, lymph nodes, and skin
- Assess vital signs, e.g., systolic blood pressure, diastolic blood pressure, and pulse, after subject has rested for at least 5 minutes, pre-dose (trough)
- Record body weight
- Perform a single 12-lead ECG at pre-dose
- Assess SAEs/AEs
- Assess changes/additions to concomitant medications

- Collect blood samples for safety assessment of Hb by local laboratory
- Prepare RBC blood smear (local laboratory) to assess for sickle cells (central laboratory)
- Urine pregnancy test (only in females of childbearing potential). Positive urine pregnancy test results need to be confirmed using a serum beta-hCG test (local laboratory assessment)
- Collect urinalysis samples for central laboratory assessment of:
 - pH, protein, glucose, ketone, RBCs, and WBCs (urinary dipstick test); quantitative measurement only if positive dipstick
 - Urinary microalbumin, creatinine, and microalbumin/creatinine ratio (spot urinary sample, morning void)
- Collect samples at pre-dose (trough) for central laboratory assessment of:
 - Haematology panel/RBC indices
 - Serum chemistry panel
 - Haemolysis markers
 - Endothelial inflammation/dysfunction markers
 - VIT-2763 PK parameters
 - Total serum iron, serum ferritin, serum transferrin, calculated TSAT, hepcidin, and erythropoietin (central laboratory assessment)
- Record VOC episodes (number of events and pain intensity (NRS: 0-10) compared to historical VOC episodes). Assess visceral infarctions as per standard of care
- Collect the ASCQ-Me forms completed by subject
- Dispense IMP at site (via IWRS). Note: The morning dose on the visit day needs to be taken at site
- Collect additional PK samples at 2 hours (±15 minutes), 4 hours (±30 minutes) and 6 hours (±30 minutes) post-morning dose (for central laboratory assessment)

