- Collect samples (2 hours post-morning dose) for total serum iron, serum ferritin, serum transferrin, calculated TSAT, hepcidin, and erythropoietin (central laboratory assessment)
- Perform a single 12-lead ECG at 2 hours (±30 minutes) post-morning dose.

- Dispense 2 copies of all of the following forms "Emotional Impact", "Pain Impact", "Sleep Impact", and "Stiffness Impact"
- Inform subject to complete 1 copy of each form 1 week after the visit, and a second copy the day before the next visit (Visit V5)
- Perform IMP accountability

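### Iron markers are drawn only before and 2 h after the morning dose, so the 4–12 h course is seen only at the trough; use the existing Visit 4 draws at 4 h and 6 h, and keep time points apart in the SAP

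*Protocol*

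**What the plan says.** Protocol Table 1, footnote 13, fixes the iron sampling: "Iron-related parameters/markers of erythropoiesis sampled at pre-dose and 2 hours post-morning dose include total serum iron, serum ferritin, transferrin, TSAT". The visit lists in Sections 8.2 to 8.6 follow it. At Visit 4 the post-dose iron instruction is "Collect samples (2 hours post-morning dose) for total serum iron, serum ferritin, serum transferrin, calculated TSAT, hepcidin, and erythropoietin", while the draws that run on to 4 h and 6 h are for drug concentration: "Collect additional PK samples at 2 hours (±15 minutes), 4 hours (±30 minutes) and 6 hours (±30 minutes) post-morning dose" (also Table 1, footnote 14).

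On timing, Section 1.4.1 reports that in Phase 1 "a temporary decrease in mean serum iron levels and a temporary decrease in mean calculated % TSAT was seen at all VIT-2763 dose levels", and places it "between 4-hours and 12-hours post-dose".

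On purpose, Section 2.3.3 attributes the lack of haematological response in the thalassaemia study to iron restriction that was not sustained between doses, and says that "different fluctuations of induced peak and trough serum iron throughout a 24-hour period (BID and TID) are explored". Section 1.4.2 draws the lesson that "PK and PD samples will needed to be collected at additional time points to fully understand the effects of vamifeport".

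SAP 5.9.1 tabulates iron markers by visit and plots them against target visit day, with no split by time point. SAP 5.1.3 averages a parameter's values when several exist on the selected day. SAP 5.8.3, by contrast, describes ECG values separately for pre-dose and 2 h.

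**The concern.** The protocol was amended because restriction between doses was thought too weak, and serum iron is its acute pharmacodynamic readout (Section 2.2). Yet nothing is measured from 2 h until the next trough, which is most of the period in which Phase 1 located the effect. If indirect bilirubin does not move, the sponsor will want to know how far iron fell after a dose and how long it stayed down. The trough answers part of that. The depth of the fall and its early duration will be unknown, although blood is being taken at two of the missing times.

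The information that is collected is also at risk. Read literally, the SAP would merge the pre-dose and 2 h iron values into one number per visit, which would remove the one within-day contrast the schedule allows.

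**Working it through.** The plan gives no figure to reproduce. The check is timing arithmetic from the dosing rules in Protocol Section 6.3.2.

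**1. Where the morning trough falls.** Hours since last dose = 24 − (hours from morning to evening dose).
- BID: 24 − 12 = 12 h (11–13 h with ±1 h on the evening dose).
- TID: 24 − 16 = 8 h (7–9 h).
- If the morning dose moves across its full 06:00–10:00 window from one day to the next, the limits widen by 4 h each way: 12 − 4 − 1 = 7 to 12 + 4 + 1 = 17 h (BID), and 8 − 4 − 1 = 3 to 8 + 4 + 1 = 13 h (TID).

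**2. Nominal iron samples inside the Phase 1 window (4–12 h after the last dose), per treatment visit.**
- Now: BID has one (12 h, at the edge); TID has one (8 h). The 2 h sample is outside.
- With 4 h and 6 h added at Visit 4: three each (BID 4, 6, 12 h; TID 4, 6, 8 h).

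**3. Longest unsampled stretch of a dosing interval**, letting the morning trough stand for the end of the interval.
- Now: BID 12 − 2 = 10 h; TID 8 − 2 = 6 h.
- With the added draws: BID 12 − 6 = 6 h; TID 8 − 6 = 2 h.
- Directly observed span on the visit day: from 2 of 24 h to 6 of 24 h.

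**4. What 4 h and 6 h can say about BID versus TID.** Cohorts 2 and 3 take the same 120 mg morning dose (Section 6.3.1), and the first dose that differs is the TID afternoon dose at 8 h. Carry-over from the evening dose, using the stated half-life of 2–5 h and assuming single-exponential decline, is 0.5^(t/half-life): 2–19% at 12 h (BID) and 6–33% at 8 h (TID). The two cohorts should therefore look broadly alike at 4 h and 6 h. These points inform depth and early duration, including 60 mg against 120 mg, more than BID against TID.

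**5. What the averaging rule does.** Let T be the on-treatment trough, P the 2 h value and B the pre-dose baseline (SAP 5.1.2). If T and P are averaged, the change reported is (T + P)/2 − B = ½(T − B) + ½(P − B), so trough and post-dose effects cannot be separated. If 4 h and 6 h values were added without an exemption, Visit 4 would be a mean of four values and Visits 3, 5 and 6 means of two, so visits would no longer be comparable.

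**6. Cost.** 24 subjects × 2 draws = 48 panels, if all 24 reach Visit 4 and placebo subjects are bled as Table 1 shows.

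**The case against.** The case for the current schedule is substantial.

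- **The trough is the right sample for the sponsor's hypothesis.** That hypothesis concerns restriction at the end of the interval. Pre-dose draws at Visits 3 to 6 measure it four times, nominally inside the Phase 1 window. The 12 h and 8 h delays are each regimen's own interval end, so the difference between them is not a confounder. This stands. A reader might infer that the trial cannot show sustained against fluctuating restriction, or that no sample meets the Phase 1 window; the dosing times support neither.
- **The 2 h sample works.** In the thalassaemia study the TSAT change at about 2 h was −26.2% (QD), −46.8% (BID) and −1.3% (placebo) (Section 2.3.3). This stands too: 2 h is informative, though it does not show the nadir.
- **Other readouts exist.** Red-cell indices are measured at every treatment visit, and SAP 5.7.3 counts subjects with at least a 5% fall in CHCM and MCHC. It would therefore go too far to say that a null bilirubin result could not be interpreted.
- **Section 2.3.3 may mean only that regimens are randomised**, not that a 24-hour iron profile is measured. That reading is fair, but Section 1.4.2 asks specifically for more pharmacodynamic time points. The previous schedule is not in the documents, so they do not show whether any were added.
- **4 h and 6 h do not separate BID from TID.** Correct (step 4); the fix must not claim otherwise.
- **Weight and timing.** This is an exploratory endpoint with 6 subjects per active cohort and descriptive analysis. SAP V2.0, of 26 April 2024, already mentions missing Visit 6 data, so a change in sampling may come too late.

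**Conclusion.** The concern holds as a gap in description, not as a failure of design. The plan supports a trough comparison and a crude 2 h versus trough contrast. It does not measure the nadir, or the course over the 10 h (BID) or 6 h (TID) between the 2 h sample and the end of the interval. Two of the missing points could be had from blood draws already scheduled, which makes this a cheap improvement worth making.

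It would be wrong to infer that the added points would give the 24-hour BID versus TID profile: the afternoon, evening and night would remain unsampled.

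The SAP issue is separate and does not depend on new samples. SAP 5.9.1 is silent on time points, so merging is what the general rule implies rather than something the SAP states outright. It needs an explicit instruction.

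The sizes rest on nominal dosing times, the Phase 1 window carrying over to sickle cell disease, and all 24 subjects attending Visit 4.

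**What to change.** **Protocol, Table 1 footnote 13 and Section 8.4:** add serum iron, transferrin/TSAT and hepcidin to the existing 4 h and 6 h draws at Visit 4. State that these points describe depth and early duration of restriction after the morning dose and are not a 24-hour comparison of BID with TID.

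**SAP 5.9.1:** report pre-dose and each post-dose iron value separately, by cohort, at every visit, as SAP 5.8.3 does for ECG. At Visit 4 show the 0, 2, 4 and 6 h profile by cohort. **SAP 5.1.3:** exempt iron markers from same-day averaging. Also assign the Day 1 2 h sample a place: SAP Table 4 has baseline ending before first intake and Visit 3 starting on Day 2, so it belongs to no window.

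**Cost:** 48 central-laboratory panels, one small extra tube at each of two existing draws, a minor amendment and a laboratory-manual change, with no new venepuncture and no longer stay. If Visit 4 collection is complete, the SAP changes still apply and need only programming. The documents do not say whether stored Visit 4 samples could be assayed.

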VIT-2763 (2-(2-{[2-(1H-benzimidazol-2-yl) ethyl] amino} ethyl)-N-[(3-fluoropyridin-2-yl) methyl]-1,3-oxazole-4-carboxamide trihydrochloride) is a small molecule, which has been identified by Vifor Pharma as a ferroportin (FPN) inhibitor acting similar to hepcidin.

FPN is the only known iron transporter in mammals mediating iron transfer into the blood stream. FPN is mainly expressed on intestinal enterocytes, spleen and liver macrophages, and hepatocytes. On the basolateral membrane of intestinal enterocytes, FPN exports the dietary iron into the plasma. On spleen and liver macrophages and hepatocytes, FPN exports endogenous iron recycled from the Hb of senescent RBCs and released from the liver stores, respectively [1]. The action of FPN is antagonised by hepcidin, a 25-amino acid peptide, which is mainly produced in hepatocytes. Its transcription is downregulated by erythropoiesis, anaemia, and hypoxia, and it is upregulated by inflammation and high systemic iron levels. Hepcidin binds to and triggers internalisation and degradation of FPN, and by this causes a rapid drop in serum iron levels [2,3].

1.1 Background of the Disease and Treatment Options

Iron is essential for cell survival. It is a key component of Hb, cytochromes, myoglobin, and of many enzymes. It is involved not only in the transport, storage, and use of oxygen, but also in major metabolic pathways. Consequently, iron homeostasis in the body is closely regulated, and imbalances may become pathogenic. Iron deficiency may result in anaemia; iron overload syndromes in siderosis, i.e., the iron deposition in organs, which may lead to multiple organ dysfunction and damage [4]. Primary iron overload syndromes arise from mutations, e.g., in genes of human haemochromatosis protein, haemojuvelin, hepcidin, transferrin receptor 2, and FPN. Secondary causes for iron overload are SCD, other inherited, or acquired anaemias, myelodysplastic syndrome, chronic liver diseases, and transfusions [5].

SCD is a multisystem disease and is one of the most common severe monogenic disorders worldwide. This often-devastating disease is associated with episodes of acute illness and progressive organ damage [6,7]. The pathophysiology of SCD arises from a single amino acid alteration in adult Hb, the expression of which is primarily limited to RBCs. The pathological single amino acid substitution (Glu to Val) at the sixth position of the β -chain of HbS results in HbS instability and polymerisation [8]. Following deoxygenation of HbS, and aggregating into polymers, the RBC changes shape ('sickles') owing to this polymer induced distortion. This distortion is the fundamental basis for the haemolytic anaemia, vaso-occlusion associated with painful events, organ dysfunction and shortened lifespan in patients with SCD [9].

The consequences of haemolysis include the immediate effects of RBC loss, such as anaemia and expansion of erythropoiesis with increased reticulocytosis. Oxidative changes in the sickle RBC promote haemolysis, depletion of nitric oxide, excess reactive oxygen species and endothelial activation. It is estimated that about one-third of haemolysis in SCD

is intravascular, owing to mechanical destruction of deformed and inelastic sickle RBCs, whereas two-thirds is extravascular, resulting from removal of abnormal sickle RBCs by the reticuloendothelial system [10].

Erythrocyte transfusion has an established role in the management of both acute and chronic complications in SCD. Transfusion corrects anaemia, decreases the percentage of HbS, suppresses HbS synthesis, and reduces haemolysis, all of which are of potential benefit. Chronic blood transfusion is inevitably associated with iron overload, although the pattern of haemosiderosis seems different to that described in thalassaemia; in particular, most iron loading occurs in the liver, with little cardiac iron deposition [11].

Curative therapies, such as haematopoietic stem cell transplantation or gene therapy are limited to a small patient population or are not yet available. Chronic transfusion is generally used for primary or secondary stroke prevention [9].

Acute pain crisis may be managed with pain medications, including opioids and may require additional in-patient or outpatient treatments, including hydration, transfusion, supplemental oxygen, and a variety of other treatments. Currently approved therapies such as hydroxyurea address some of the pathologies in SCD. Hydroxyurea is used to reduce the number of acute pain crises in those with frequent or severe crises and in those with a history of acute chest syndrome or severe anaemia. Within the past several years, a few new treatment options, such as L-glutamine, crizanlizumab, and voxelotor, have gained regulatory approval in the United States; however, the evidence for the clinical effectiveness of these treatments has been controversial [12].

Drugs that target the broader sequelae of SCD are needed, and prevention of haemolysis might provide a novel therapeutic option. Overt iron deficiency in patients with SCD has been associated with reduction of HbS in sickle RBCs and decreased markers of haemolysis [13,14].

VIT-2763 is developed by Vifor Pharma as a novel oral drug targeting FPN, and as such for the treatment of secondary iron overload and conditions in which iron metabolism is involved: ineffective or otherwise disturbed erythropoiesis, including (but not limited to) hereditary haemochromatosis, haemoglobinopathies (e.g., thalassaemia and SCD), or myeloproliferative/dysplastic disorders (e.g., polycythaemia vera and myelodysplastic syndrome, respectively). Furthermore, the oral FPN inhibitor VIT-2763 has shown positive results on haemolysis, haemodynamics, and prevention of vaso-occlusion in a model of SCD [15].

Since no FPN inhibitors or hepcidin-mimetic drugs are yet available for the treatment of iron loading anaemias including SCD, VIT-2763 would be considered as a first-in-class drug.

